9.7.4 Exploratory Analysis

In addition to the concurrent control arm, a historical population dating from after the start of the pandemic but before the availability of COVID-19 vaccines will be identified to contextualize the results and assess the potential impact of different time periods for the analysis. The historical population will be defined as people during the periods from July to September (when SARS-CoV-2 testing was more complete than at the beginning of the pandemic, but there was relatively little

SARS-CoV-2 circulation) and September to December 2020 (when there was increased SARS-CoV-2 circulation).

The event's incidence rates in the historical population will be measured in two ways:

1) National rates of events from July to September and September 1st to December 7th, 2020, to loss to follow-up, or death whichever is earlier and

2) Regional rates of events associated with COVID-19 during periods considered to be the 1st and 2nd wave of infection (for all cause outcome events). This will be conducted in each region in England but not before July 1st 2020 (as limited COVID-19 testing was available before July 2020). The exact timing of each wave of infection by regions in England will be determined during the analysis phase.

Contrary to the concurrent control arm, events' rates in the historical population are not impacted by different age distribution but may be impacted by isolation measures (e.g. lockdown) and waves of infections. Therefore, regions and relevant time periods will be taken into account in terms of waves of infection /lockdown. The exact date of start and end of each wave of infection by regions will be determined during the analysis phase.

When taking into account waves of infection, for COVID-19 related outcomes, the historical population will be followed from the designated date of start of 2nd wave of infection by regions in England (but not before September 2020), when COVID-19 test was more complete, to the end of the 2nd wave, loss to follow-up, or death whichever is earlier. For all-cause outcomes, the historical population will be followed from the designated date of start of 1st wave or 2nd of infection by regions in England to the end of the corresponding wave, loss to follow-up, or death whichever is earlier.

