The Hospital Episode Statistics (HES), Secondary Uses Service (SUS), General Practice Extraction Service data for pandemic planning and research (GDPPR), and Office of National Statistics (ONS) data may include information on COVID-19 infection through specific COVID-19 diagnosis codes. Using a combination of both COVID-19 SGSS/NPEX and diagnosis codes from HES, SUS, GDPPR, and ONS allow capturing the COVID-19 infection status for all study participants. Since testing for COVID-19 and its capture was not complete at the beginning of the pandemic but significantly improved later, restriction of the study period from July 2020 or the 2nd wave of infection by regions in England, whichever is later, for determining COVID-19 related events in the historical population is needed. Medically attended COVID-19 will come from ORCHID, GDPPR, Emergency Care Data Set (ECDS) and HES. Emergency department visits will come from ECDS. SARS-CoV-2 variants will come from COG UK. Data on HCRU and associated cost will come from HES using the Health Resource Grouper (HRG) and primary care attendance and medication costs. Long COVID will come from ORCHID and HES.

|--|

Variables		Data source	Comments
Hospitalization	Date	HES for curated data	6-8 weeks lag for HES
	Frequency	SUS for more recent raw data	SUS is updated weekly
	Duration	HES APC for combined	with a maximum of 2 weeks lag
ICU admission	Date	CC for ICU specific data	
	Frequency		
	Duration		
Death	Date	ORCHID/GDPPR for date	2 weeks lag
	Cause of death	ONS for cause of death	6 weeks lag
Medically attended COVID-19		ORCHID, GDPPR, ECDS, HES	
COVID-19 infection	Positive RT-PCR test; date	SGSS for first positive test in hospital and community NPEX for all positive/negative test in the community	Daily update
	ICD-10/SNOMED codes for COVID	HES, ONS, GDPPR	
SARS-CoV-2 variants of interest		COG UK	
Long COVID		ORCHID, HES	
HCRU and cost		HES & HRG	
		ICU datasets	
		Primary care attendance & costs	

APC: Admitted Patient Care; CC: Critical Care COG UK: COVID Genomics UK Consortium; ECDS: Emergency Care Data Set; GDPPR: General Practice Extraction Service data for pandemic planning and research; HES: Hospital Episode Statistics; HRG: Health Resource Grouper; ICU: Intensive Care Unit; NPEX: National Pathology Exchange; ONS: Office for National Statistics; ORCHID: Oxford-Royal College of General Practitioners Clinical Informatics Digital Hub; SGSS: COVID-19 Second Generation Surveillance System; SUS: Secondary Uses Service.

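### In the exploratory historical-population analysis, the 1st-wave rates conflict with the July 2020 floor, and wave-based follow-up has no stop at vaccine start

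*Protocol*

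**What the plan says.** Protocol 9.7.4 sets up a historical comparison: "a historical population dating from after the start of the pandemic but before the availability of COVID-19 vaccines will be identified". It names two periods. The first is given by "The historical population will be defined as people during the periods from July to September", which the section describes as having fairly complete testing and little circulation. The second is September to December 2020, described as having more circulation.

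Rates are then to be measured in two ways.

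- National: "National rates of events from July to September and September 1st to December 7th, 2020".
- Regional: by 1st and 2nd wave, with the limit "This will be conducted in each region in England but not before July 1st 2020". The reason given is that testing was limited before July 2020. The item speaks of events associated with COVID-19 but adds in brackets that the waves are for all-cause outcomes.

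The last paragraph of 9.7.4 gives the follow-up rule when waves are used. COVID-19 related outcomes start at the regional 2nd wave, but not before September 2020, and run "to the end of the 2nd wave, loss to follow-up, or death whichever is earlier". For all-cause outcomes the population is "followed from the designated date of start of 1st wave or 2nd of infection by regions in England", to the end of that wave, loss to follow-up or death. Wave dates are left to the analysis phase.

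Section 9.3.2 gives another start rule for COVID-19 related events in this population: "restriction of the study period from July 2020 or the 2nd wave of infection by regions in England, whichever is later".

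**The concern.** Two of these rules do not fit the rest of the section.

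First, the July floor and the 1st-wave request pull against each other. With the floor applied, a 1st-wave rate rests on time that the section itself calls low-circulation. Without it, as in the last paragraph, the rate rests on a different window. Two analysts following different sentences would report different 1st-wave rates. The reason for the floor, incomplete testing, concerns COVID-19 related outcomes. It does not bear on all-cause hospitalization, ICU admission or death.

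Second, the wave-based follow-up rule lets person-time run to the end of the 2nd wave, whenever that is. The population is meant to be pre-vaccine, but nothing in the rule stops at vaccine start or censors at vaccination.

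Table 3 makes this population the unvaccinated comparator for an exploratory VE objective, and 9.7.4 and 9.11.1 use it to put the main results in context. Vaccinated person-time in that comparator would lower its event rate if the vaccines work, and so pull the exploratory VE down.

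**Working it through.** The protocol gives no event count, rate or wave date for this analysis, so there is no figure to reproduce. The check sets the date rules side by side and counts calendar days, both ends included.

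**1. The rules**

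| Rule | Start | Stop |
|---|---|---|
| Population definition (9.7.4) | July 2020 | before vaccines are available |
| National rates (9.7.4) | July 2020; 1 September 2020 | no end day for the first period; 7 December 2020 for the second |
| Regional wave rates (9.7.4) | 1st or 2nd wave, not before 1 July 2020 | end of wave |
| Wave follow-up, COVID-19 related (9.7.4, last paragraph) | 2nd wave, not before September 2020 | end of 2nd wave |
| Wave follow-up, all-cause (9.7.4, last paragraph) | 1st or 2nd wave, no floor | end of that wave |
| COVID-19 related events (9.3.2) | later of July 2020 and 2nd wave | not stated |
| Concurrent matching (9.7.1) | 8 December 2020 | – |

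**2. First wave.** The third and fifth rows cannot both hold for a 1st wave that began before 1 July 2020. On the section's own description of July to September, little or none of a first wave lies after the floor.

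**3. Stop date.** National rates end the day before concurrent matching starts. The wave rules have no matching limit. Vaccine-era share = (days after 7 December 2020) ÷ (days from wave start to wave end). The 2nd-wave start of 1 September 2020 and the wave ends below are assumptions, because the protocol gives neither.

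| Assumed end of 2nd wave | Days in wave | Days after 7 December | Share |
|---|---|---|---|
| 7 December 2020 | 98 | 0 | 0% |
| 31 December 2020 | 122 | 24 | 20% |
| 31 January 2021 | 153 | 55 | 36% |
| 28 February 2021 | 181 | 83 | 46% |
| 31 March 2021 | 212 | 114 | 54% |

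These are shares of calendar time. The share of person-time that is actually vaccinated would be smaller and cannot be computed from the protocol.

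**4. September.** If the first period runs through 30 September, it has 31 + 31 + 30 = 92 days. The second has 30 + 31 + 30 + 7 = 98 days, and the whole span from 1 July to 7 December has 160. The overlap is 92 + 98 − 160 = 30 days, which is 30/92 = 33% of the first period and 30/98 = 31% of the second. If the first period ends on 31 August, it has 62 days, 62 + 98 = 160, and the overlap is 0. The text does not say which is meant.

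**5. Start for COVID-19 related outcomes.** The September floor in 9.7.4 and the rule in 9.3.2 give the same start if a region's 2nd wave begins in September or later. They differ only if it is dated to July or August.

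**The case against.** The best defence is that the general definition already settles most of this. Sections 9.2.1, 9.7.4 and 9.11.1 all describe the population as before vaccination, so a sensible analyst would stop at vaccine start even though the follow-up sentence does not say so. Section 9.1 links vaccination to the 3rd wave, so in the protocol's own terms the 2nd wave need not reach December. This stands in part: the harm is conditional on how waves are dated. It does not remove the gap. The operative rule lists its stopping events and omits this one, and no section says that the 2nd wave ended by 7 December 2020.

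September is also defensible. An explicit 1 September start for the second period suggests a split at that date. The two rates are reported separately, so no double counting follows. A reader might infer that the low-circulation rate is inflated by a known factor. The document does not support that: it would need both the whole-month reading and a ratio of September to summer rates that the protocol does not give.

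The start rules in 9.3.2 and 9.7.4 are nearly compatible, because 9.3.2 takes the later of its two dates.

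Finally, Table 3 classes the analysis as exploratory, and 9.2.1 calls it descriptive. That limits the weight of the point. None of these arguments answers the conflict between the July floor and the unfloored 1st-wave follow-up.

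**Conclusion.** The point holds for two stated rules. The 1st-wave rate has two incompatible windows within 9.7.4. Wave-based follow-up lacks the stop at 7 December 2020 that the population definition implies and the national rates apply. The unstated end day for July to September and the differing start rules for COVID-19 related outcomes are secondary points of wording.

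The size of the second problem depends on wave dates fixed later. With an assumed wave start of 1 September 2020, the vaccine-era share of calendar time is 0% if the wave ends by 7 December and rises to 54% if it ends on 31 March 2021.

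A reader might infer that the historical rates would be wrong, or that the main VE results are at risk. The documents support neither. The exploratory rates could be inconsistent or include vaccine-era time. The primary and secondary VE estimates use matched concurrent controls from 8 December 2020 and do not depend on these dates.

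**What to change.** Before analysis, amend 9.7.4 and 9.3.2 as follows.

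- End all historical follow-up at the earliest of wave end, 7 December 2020, loss to follow-up or death. No censoring at vaccination is then needed.
- Apply the testing-based floor to COVID-19 related outcomes only, with one date used in both sections. Exempt all-cause outcomes from it, and widen the opening definition of the population to match. Alternatively, drop the 1st wave.
- State in the regional-rate item which outcomes it covers.
- End the first period on 31 August 2020, so that it meets the second without overlap.

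The cost is wording in two sections and a shorter historical window wherever a 2nd wave runs past 7 December. The primary and secondary analyses do not change.

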The RAVEN study extension adds a description of proportion and the risk profile of the people at risk of COVID due to either a suboptimal vaccine response or from being ineligible for vaccination. People who are immunocompromised are the primary population of interest. In addition, we will conduct an analysis of HCRU and health care cost for the whole population and for risk groups identified as having a suboptimal vaccine response. Furthermore, we will assess VE against a wider range of outcomes, and assess VE of booster/other additional vaccine doses. Finally, we will explore the impact of vaccination on household incidence/transmission, using an established method (de Lusignan et al, 2020a; de Lusignan et al, 2020b) and on long COVID.

Table 3. Primary, secondary, exploratory and RAVEN extension objectives

Objectives	Outcome measure
Primary	Primary
-To assess the effectiveness of the Oxford/AstraZeneca COVID-19 vaccine	-Hospitalization associated with COVID-19
among people who receive at least one dose of the vaccine; overall and by	-Admission to ICU associated with COVID-19
a)number of doses	-Mortality associated with COVID-19
b) age group	
c) comorbidity status	Secondary
d) time period after each dose	-All-cause hospitalizations
e) interval between doses	-All cause admission to ICU
	-All-cause mortality
Secondary	Same as above
-To assess the effectiveness of other (e.g. mRNA) COVID-19 vaccines among	
people who received at least one dose, overall and by	
a) number of doses	
b) age group	
c) comorbidity status	
d) time periods after each dose	
e) interval between doses	
Exploratory	Same as above
-To assess the effectiveness of the Oxford/AstraZeneca COVID-19 vaccine and	
other COVID-19 vaccines among people who receive at least one dose of the	
vaccine, using a historical unvaccinated population as comparator.	

RAVEN extension objectives:	
-To describe the population at risk of COVID due to being ineligible for a COVID-19 vaccines.	
-To explore the population at risk of COVID due to a suboptimal response (breakthrough case) by predicting breakthrough cases, identifying susceptible sub-populations, predicting their time to vaccine waning and identifying predictors of receiving AZ or other booster. People who are immunocompromised are the primary population of interest, in our exploration of suboptimal vaccine response.	 Breakthrough case Primary outcomes in breakthrough cases Time to vaccine waning AstraZeneca COVID-19 booster vaccination

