9.2 Setting

9.2.1 Study Population

The study population of this study is people in England who have received at least one dose of the Oxford/AstraZeneca COVID-19 vaccine from January 2021 onwards (the AstraZeneca vaccine arm) or at least one dose of another (e.g. mRNA) COVID-19 vaccine from December 2020 onwards (the Other vaccine arm) and people in England who were not vaccinated with any COVID-19 vaccine during the same time period (concurrent control arm) who will be matched to the vaccinated individuals by age, gender, GP practice (NHS region), and comorbidity (see Section

9.7.1 for a description of matching). Study participants of any age will be considered. For the vaccinated individuals, the study's index date is the date of vaccination of the 1st dose.

Concurrent controls who become vaccinated will be censored at date of vaccination and, then may re-enter the study as newly vaccinated individuals. An appropriate control group will be identified for the booster dose evaluation.

To contextualize, we will describe the impact of SARS-CoV2 on the unvaccinated English population, prior to the availability of COVID-19 vaccines. We will conduct a descriptive analysis of COVID-19 of this historical population of unvaccinated persons in England.

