9.5 Study Size

The NHS Digital database comprises data from the national registries of vaccination and hospitalization with linkage to the CMR, lab, and mortality data. It is the largest dataset possible for England and covers all regions. As of early March 2021, near 20 million people in England have been vaccinated with at least 1 dose of any COVID-19 vaccines. According to a recent study in Scotland (Vasileiou et al 2021), the Oxford/AstraZeneca vaccine have been used by the majority of the 75+ years old age group and by a significant proportion of the 60-65- and 70-75-years old age groups.

Based on the preliminary count of the cohort of VE from ORCHID in collaboration with PHE (N=5.4 million), as of 7/4/2021, 42.1% of the population have received a COVID-19 vaccine. Overall, 91% of people 80 years and older, 91% of people 65-79 years old, and 79% of people aged 16-64 years old in risk groups were vaccinated. Of those vaccinated, 38% has received the Oxford/AstraZeneca COVID-19 vaccine, i.e. more than 7 million people. It is expected that almost all of England's COVID-19 vaccination data are included in the NHS Digital databases representing the best option for this type of study. Given a large number of people vaccinated with the Oxford/AstraZeneca COVID-19 vaccine and the use of the national database, the study should have sufficient power to address the study objectives.

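### Section 9.7.4 sets age aside for the historical population, so the exploratory historical VE in Table 3 has no stated age control and an overall estimate would most likely be too low early in the roll-out

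*Protocol*

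**What the plan says.** - **9.7.4, definition.** "The historical population will be defined as people during the periods from July to September" 2020 and from September to December 2020. No age limit, matching or standardisation is given, and 9.2.1 adds for the study at large: "Study participants of any age will be considered".
- **9.7.4, on age.** In contrast to the concurrent control arm, the section says, event "rates in the historical population are not impacted by different age distribution". The sentence goes on to allow for isolation measures and infection waves. The consequence drawn is that "regions and relevant time periods will be taken into account in terms of waves of infection /lockdown". Age is not named.
- **Section 8, Table 3.** The exploratory objective is to assess the effectiveness of both vaccine groups among people with at least one dose of the "vaccine, using a historical unvaccinated population as comparator". It uses the same outcomes as the primary and secondary objectives. Those two objectives list a breakdown by age group; this one does not.
- **9.2.1, on the same population.** "We will conduct a descriptive analysis of COVID-19 of this historical population of unvaccinated persons in England". Sections 9.7.4 and 9.11.1 likewise describe its purpose as giving context.
- **9.7.1.** Matching on age band, and the Poisson model that adjusts for it, are defined for vaccinated persons and their concurrent controls. The historical population is not in that matched dataset.
- **9.5, at 7 April 2021.** "42.1% of the population have received a COVID-19 vaccine. Overall, 91% of people 80 years and older, 91% of people 65-79 years old".

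**The concern.** Section 9.7.4 gives a reason for leaving age out of the historical comparison, and the reason does not support that step. Whether a population was depleted of older people is one question. Whether its age mix matches that of the group it is compared with is another, and only the second decides whether a rate ratio is confounded by age. Elsewhere the protocol says that the campaign began with the oldest (9.1), that younger people are expected to have lower hospitalization and death, and that age adjustment is critical (9.11.1, said of the concurrent arm).

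At stake is a secondary reading of the study. The historical result is meant to put the primary VE in context. If an overall historical VE came out well below the matched VE because the vaccinated were older than the comparator, readers could take a structural artefact for a discrepancy. A related question is which calendar period may serve as comparator for COVID-19 outcomes, because 9.7.4 itself describes July to September 2020 as a time of little circulation.

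**Working it through.** **Is there a figure to reproduce?** No. The protocol states no VE, power or precision for the historical comparison. What follows is an illustration of age confounding alone.

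**Inputs from 9.5** (any vaccine, ORCHID cohort of 5.4 million, 7 April 2021): overall coverage V = 0.421; coverage at 65+ c = 0.91, since 65-79 and 80+ are both 91%.

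**Assumptions, not in the protocol:** share of people aged 65+ in the population, s = 0.15 to 0.22; event rate at 65+ relative to under 65, R = 3 to 20; the same true VE at all ages; no difference in background risk between the calendar periods.

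**Formulas**
- Share of 65+ among the vaccinated: w = c × s / V
- Factor on the crude rate ratio: F = (wR + 1 − w) / (sR + 1 − s)
- Apparent VE = 1 − (1 − true VE) × F

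**One case in full** (s = 0.185, R = 10): w = 0.91 × 0.185 / 0.421 = 0.40. F = (0.40 × 9 + 1) / (0.185 × 9 + 1) = 4.60 / 2.665 = 1.73. A true VE of 80% shows as 1 − 0.20 × 1.73 = 65%. A vaccine with no effect would show −73%.

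**Range, factor and apparent VE when the true VE is 80%**

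| s | w | R = 3 | R = 5 | R = 10 | R = 20 |
|---|---|---|---|---|---|
| 0.15 | 0.324 | 1.27, 74.6% | 1.44, 71.3% | 1.67, 66.7% | 1.86, 62.8% |
| 0.20 | 0.432 | 1.33, 73.4% | 1.52, 69.7% | 1.75, 65.1% | 1.92, 61.6% |
| 0.22 | 0.476 | 1.35, 72.9% | 1.54, 69.1% | 1.77, 64.6% | 1.94, 61.3% |

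With April 2021 coverage, 80% therefore shows as about 61% to 75%.

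**Later in the roll-out** (assumed: overall coverage 70% to 80%, 95% at 65+, s = 0.18, R = 5 to 20): w falls to 0.214 to 0.244 and F to 1.08 to 1.28. A true 80% shows as 74.5% to 78.4%, roughly 75% to 78%.

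**Effect of standardising.** Weighting both groups to the same age distribution makes F = 1. With s = 0.18 and R = 10 the standardised rate ratio is 0.20, so the true 80% is recovered. Differences in circulation and lockdown remain.

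**Comparator periods, side by side**
- 9.7.4, first method: national event rates for July to September and for 1 September to 7 December 2020, with no separation of COVID-19 from all-cause outcomes.
- 9.3.2: COVID-19 related events in the historical population are restricted to July 2020 or the regional second wave, whichever is later.
- 9.7.4, last paragraph: when waves are taken into account, COVID-19 outcomes start at the second wave and not before September 2020.

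The September floor is tied to the wave-based analysis. The national rates keep July to September without saying whether COVID-19 outcomes are included, and that does not sit easily with 9.3.2.

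**The case against.** **The sentence has a sound reading.** Sections 9.1 and 9.11.1 explain that few older people remained unvaccinated, so the concurrent arm may lean young. Against that background, 9.7.4 can be read as saying that the pre-vaccine population was not depleted in this way, which is correct. A reader might infer that the protocol claims the historical and vaccinated age mixes are equal; it does not say so. What stands against the sentence is the step taken from it: only region and period are then taken into account.

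**Age is handled in general terms elsewhere.** Section 9.1 plans age-stratified event rates, and 9.7.1 plans rate, rate ratio and VE tables for each study cohort and per age group. Applied to the historical population, these would largely avoid the bias. Neither place names that population, though, and the sentence in 9.1 closes a paragraph about the concurrent arm.

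**No crude historical VE is fixed.** A reader might infer that the protocol commits to an unadjusted all-age estimate. It does not: 9.7.4 specifies rates and gives no VE estimator, and the method may properly be left to the analysis plan. The point therefore rests on a stated rationale that leads away from age control and on two sections that disagree about the purpose. It does not rest on missing detail.

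**July to September.** A reader might infer that a strongly negative VE against this period is planned. No section names it as a VE denominator, nothing in the documents allows such a value to be calculated, and the wave-based analysis already excludes it for COVID-19 outcomes. Only the national rates remain unclear.

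**Size.** The age share and rate ratio are assumptions, and the coverage figures are one early snapshot for any vaccine, so the AstraZeneca arm's own age mix is unknown. The cohort later extends to younger ages and the bias shrinks. Differences in circulation could move the net result either way. All of this stands.

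**Conclusion.** The point holds in limited form. The statement in 9.7.4 is true only in that the pre-vaccine population had not been depleted of older people. It does not justify leaving age out of a comparison with arms vaccinated oldest first. Table 3 presents that comparison as a VE objective, 9.2.1 presents it as description, and the age control that is specified does not reach it.

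An overall historical VE would be confounded by age, most likely downward early in the roll-out. The sizes above are illustrations: they rest on the assumed 65+ share and age rate ratio, on equal VE across ages, and on equal background risk between periods. The early range uses the April 2021 coverage in 9.5; the later range also assumes the coverage itself.

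A reader might infer that the main result is at risk. It is not: the analysis is exploratory, and the primary VE comes from the matched concurrent comparison. The change is still worth making, because the historical result is meant to be read beside the primary one.

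**What to change.** 1. **9.7.4:** replace the sentence on age. Say that the historical population was not depleted of older people by vaccination, but that its age mix differs from that of the vaccinated arms, so age must be accounted for alongside region and period.
2. **Table 3, 9.2.1 and 9.7.4:** state one purpose. Either restate the exploratory objective as descriptive or, if a historical VE is kept, report it only by age band or directly standardised to each vaccinated arm's distribution of age band, gender and region. Add the multimorbidity measure only if it is validated: 9.4 notes that some Cambridge Multimorbidity Score component codes do not exist in GDPPR and allows for an alternative measure.
3. **9.7.4 and 9.3.2:** reconcile the national July to September rates with the start dates given for COVID-19 outcomes. Use July to September rates for COVID-19 outcomes as description only, not as a VE comparator.

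**Cost:** protocol wording and, if a historical VE is kept, one standardisation step. Age, gender and region are already listed in Table 6, so no new data are needed. The downside is that the July to September contrast for COVID-19 outcomes becomes descriptive. Standardising removes the age component only; differences in circulation and lockdown must still be stated as limits.
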